**6.0 Registration Procedures**

6.1 To register a patient, access the Mayo Clinic Cancer Center (MCCC) web page and enter the registration/randomization application. The registration/randomization application is available 24 hours a day, 7 days a week. Back up and/or system support contact information is available on the Web site. If unable to access the Web site, call the MCCC Registration Office at [REDACTED] between the hours of 8 a.m. and 4:30 p.m. Central Time (Monday through Friday).

The instructions for the registration/randomization application are available on the MCCC web page [REDACTED] and detail the process for completing and confirming patient registration. Prior to initiation of protocol treatment, this process must be completed in its entirety and a MCCC subject ID number must be available as noted in the instructions. It is the responsibility of the individual registering the patient to confirm the process has been successfully completed prior to release of the study agent. Patient registration via the registration/randomization application can be confirmed in any of the following ways:

- Contact the MCCC Registration Office [REDACTED]. If the patient was fully registered, the MCCC Registration Office staff can access the information from the centralized database and confirm the registration.
- Refer to "Instructions for Remote Registration" in section "Finding/Displaying Information about A Registered Subject."

6.2 Correlative Research

A mandatory correlative research component is part of this study. The patient will be automatically registered onto this component (see Sections 3.19c, 14.0, and 17.0).

6.3 Documentation of IRB approval must be on file in the Registration Office before an investigator may register any patients.

In addition to submitting initial IRB approval documents, ongoing IRB approval documentation must be on file (no less than annually) at the Registration Office (fax: [REDACTED]). If the necessary documentation is not submitted in advance of attempting patient registration, the registration will not be accepted and the patient may not be enrolled in the protocol until the situation is resolved.

When the study has been permanently closed to patient enrollment, submission of annual IRB approvals to the Registration Office is no longer necessary.

6.4 Prior to accepting the registration, registration application will verify the following:

- IRB approval at the registering institution

- Patient eligibility
- Existence of a signed consent form
- Existence of a signed authorization for use and disclosure of protected health information

At the time of registration, the following will be recorded:

- Patient has/not given permission to store and use his/her sample(s) for future research of CLL/NHL at Mayo.
- Patient has/not given permission to store and use his/her sample(s) for future research to learn, prevent, or treat other health problems.
- Patient has/not given permission for MCCC to give his/her sample(s) to researchers at other institutions.

- 6.5 Treatment cannot begin prior to registration and must begin  $\leq$  14 days after registration.
- 6.6 Pretreatment tests/procedures (see Section 4.0) must be completed within the guidelines specified on the test schedule.
- 6.7 All required baseline symptoms (see Section 10.6) must be documented and graded.
- 6.8 Treatment on this protocol must commence at Mayo Clinic Rochester, Mayo Clinic in Florida, or Mayo Clinic in Arizona under the supervision of a Hematologist.
- 6.9a Study drug is available on site.
- 6.9b **Continuation Phase (Combination Treatment with MK-3475 and Ibrutinib/Idelalisib):** To register a patient fax [REDACTED] a completed continuation phase eligibility checklist to the Registration Office between 8 a.m. and 4:30 p.m. central time Monday through Friday.

## 7.0 Protocol Treatment

### 7.1 Treatment Schedule for all three arms

Agent	Dose Level	Route	Day	Cycle Length
MK-3475	200 mg	IV	Day 1	
CLL/SLL patients only: Bactrim DS*	1 tablet once daily	Oral	Three times per week while on treatment	21 days

\*If a patient has sulfa allergy or could not tolerate Bactrim, alternative PCP prophylaxis is allowed at the discretion of treating provider. For patients continuing on combination therapy, PCP prophylaxis is optional. Bactrim can be changed to alternative PCP prophylaxis.

**Note:** Tumor lysis syndrome has not been observed with MK-3475 therapy. Standard prophylaxis for tumor lysis syndrome can be considered prior to therapy.

**Note:** Each cycle of treatment is 21 days. If patient experienced adverse events which required dosing delay (see Section 8.0), the new dosing interval (increased interval) can be defined as a new cycle length. If CLL or NHL patients have achieved CMR/CR/CRi (MRD negative CR for CLL patients) confirmed by bone marrow or CT/PET evaluation, patients could continue the treatment for 2 more cycles and stop the treatment at the discretion of the treating provider. If patient experiences disease relapse after stopping therapy due to CMR/CR, the previous treatments can be restarted. The designed maximum length of treatment is 12 months (365 days).

Note: If patient is continuing to benefit from treatment after 12 months, they may continue to receive treatment up to 24 months at investigator/sponsor discretion

### 7.2 Timing of Dose Administration for all three arms

Trial treatment should be administered on Day 1 of each cycle after all procedures/assessments have been completed as detailed on the test schedule (Section 4.0). Trial treatment may be administered up to 2 days before or 7 days after the scheduled Day 1 of each cycle due to administrative reasons.

**Note:** For patients who tolerated therapy and have clinical benefits, they will be followed at each cycle for the first 6 months. Clinical response will be evaluated at 3 and 6 months. After 6-months of therapy, responsive or stable patients can be followed every other cycle by treating physician/provider until one year of total duration of therapy. However, patient will be followed by nurse at each cycle of treatment for adverse event assessment. They will be seen as needed by provider. All patients who received at least 6 months of therapy and shown clinical benefit will be evaluated again at 12 months for clinical response. For patients continuing therapy beyond 12 months, the above schedule is recommended. Further formal response evaluation is only required if there is clinical sign of disease progression. Other response evaluation is per discretion of treating physician.

### 7.3 For CLL patients with or without Richter's transformation (Arm A and Arm C), if a patient developed progressive disease (not tumor flare) at any time of the single-agent (MK-3475) therapy, or has stable disease without partial remission at the response

evaluation at month 3 of the single-agent (MK-3475) therapy, a commercially available FDA-approved CLL signal inhibitor can be added to MK-3475 (remain at the dose 200mg IV every 3 weeks). In this clinical scenario, if the patient had not used Ibrutinib in the past, Ibrutinib is recommended to be added using the standard FDA approved dose. However, the dose of Ibrutinib can be modified by treating physician based on concomitant medications or other clinical status. If the patient had progressed or had intolerable adverse events on Ibrutinib, Idelalisib is recommended to be added using the standard FDA approved dose. The dose of Ibrutinib or Idelalisib can be reduced/adjusted due to adverse events or concomitant medications according to the package inserts of the individual agent. If the patient had used both Ibrutinib and Idelalisib in the past, it is at the discretion of investigator/treating physician to decide which FDA-approved oral CLL therapy to use according to the package inserts of the individual agent and clinical status of the patient.

**Treatment Schedule for Combination Therapy with MK-3475 and Ibrutinib**

Agent	Dose Level	Route	Day	Cycle Length
MK-3475	200 mg	IV	Day 1	21 days**
Ibrutinib	420 mg	Oral	Once daily	

\*\*If the dosing interval was increased due to adverse events while receiving single-agent MK-3475, continue with the increased dosing interval the patient was receiving for the last cycle of single-agent MK-3475

**Treatment Schedule for Combination Therapy with MK-3475 and Idelalisib**

Agent	Dose Level	Route	Day	Cycle Length
MK-3475	200 mg	IV	Day 1	21 days**
Idelalisib	150 mg	Oral	Twice daily	

\*\*If the dosing interval was increased due to adverse events while receiving single-agent MK-3475, continue with the increased dosing interval the patient was receiving for the last cycle of single-agent MK-3475.

**7.4 For patient who received ibrutinib previously:**

Note: due to the observed ibrutinib withdrawal syndrome in selected CLL patients who had received ibrutinib before, steroid use in the format of 0.5 mg to 2 mg per kilogram body weight prednisone or equivalent is allowed with a gradual taper to overcome the ibrutinib withdrawal syndrome. The duration of high dose steroid use should be within the first 1-3 months when patients were off ibrutinib

**7.5 If CLL or NHL patients have achieved CMR/CR (MRD negative CR for CLL patients) confirmed by bone marrow or CT/PET evaluation, patients could continue the treatment for 2 more cycles and stop the treatment at the discretion of the treating provider. If patient experiences disease relapse after stopping therapy due to CMR/CR, the previous treatments can be restarted. The designed maximum length of active treatment with MK-3475 is 12 or 24 months.**

**7.6 Total duration of treatment including both single-agent and combination therapy is a maximum of 12 months. If the patient remains on cycles with a length of 21 days without treatment delays, this will be 17 cycles total. If the cycle length is increased due to dosing frequency changes or dose delays occur, the number of cycles will be reduced to not exceed 12 months (365 days) of treatment total. NOTE: If patient is continuing to benefit from treatment after 12 months, they may continue to receive treatment up to a total duration of 24 months including both single-agent and combination therapy at**

investigator/sponsor discretion.

7.7 At the end of the trial therapy with MK-3475, signal inhibitor can be continued or stopped at the discretion of the treating physicians.

## 8.0 Dose modification based on Adverse Events

### 8.1 MK-3475 Dose Levels

Dose Level	MK-3475**
0*	200 mg IV Day 1 every 21 days

\*Dose level 0 refers to the starting dose.

\*\*If dose modifications are needed, the dosing interval may be increased by 7 days each time, the maximal dosing interval allowed is 8 weeks.

Note: This study will not allow dose reduction of MK-3475, only dose interval changes

8.2 Arms A and C Dose Modifications – NOTE: Dose hold/modification of Ibrutinib or Idelalisib will be based on the package insert of the individual medicine. If the patient is on a moderate cytochrome P450 inhibitor or inducer (see Appendix VII), caution is recommended and close monitoring of toxicity or efficacy of therapy is warranted. Providers should consult the package insert for recommendations on dose adjustment in the setting of drug interactions. In case an adverse event cannot be easily attributed to either MK-3475 or the signal inhibitor, strongly recommend to discuss with study chair and/or sponsor for subsequent decision.

8.3 MK-3475 Dose Modifications only-see table below. In case an adverse event cannot be easily attributed to either MK-3475 or the signal inhibitor, strongly recommend to discuss with study chair and/or sponsor for subsequent decision.

→ → Use the NCI Common Terminology Criteria for Adverse Events (CTCAE) version 4.0* unless otherwise specified ← ←			
CTCAE System/Organ/Class (SOC)	ADVERSE EVENT (at least possibly related)	AGENT	ACTION**
AT TIME OF RETREATMENT			
Gastrointestinal disorders 	Enterocolitis Grade 2	MK-3475	Hold study treatment and consider infection evaluation with C. diff toxin. If rule out c.diff, anti-diarrheal treatment should be started. The recommended dose of loperamide is 4 mg at first onset, followed by 2 mg every 2-4 hours with oral hydration until diarrhea free (maximum 16 mg/day). If symptoms are persistent for more than one week or complicated with rectal bleeding, GI consultation and endoscopy is recommended. Systemic corticosteroids or budesonide 9 mg daily should be initiated (e.g., 0.5 mg/kg/day of prednisone or equivalent). When symptoms improve to Grade 1 or less, corticosteroid taper should be started. If AE improves to grade 1 or less within 4 weeks, study treatment should be restarted at the same dose with the same cycle length for the first occurrence. The cycle

			interval will increase by one week for each occurrence of the same adverse events. If the treatment is delayed $\geq$ 8 weeks from last therapy, study treatment should be discontinued and go to observation if at least 2 cycles of therapy were given, otherwise, go to event monitoring.
--	--	--	--

→ → Use the NCI Common Terminology Criteria for Adverse Events (CTCAE) version 4.0* unless otherwise specified ← ←			
CTCAE System/Organ/Class (SOC)	ADVERSE EVENT (at least possibly related)	AGENT	ACTION**
AT TIME OF RETREATMENT			
Gastrointestinal disorders	Enterocolitis $\geq$ Grade 3		Discontinue study treatment, GI consultation and endoscopy is recommended. Go to observation if $\geq$ 2 cycles were given, otherwise go to event monitoring. Treatment with systemic corticosteroids should be initiated at a dose of 1 to 2 mg/kg/day of prednisone or equivalent. When symptoms improve to Grade 1 or less, corticosteroid taper should be started.
Respiratory, thoracic and mediastinal disorders 	Pneumonitis	MK-3475	Subjects with symptomatic pneumonitis should immediately stop receiving study treatment and have an evaluation. The evaluation may include bronchoscopy and pulmonary function tests to rule out other causes such as infection. If the subject is determined to have study drug associated pneumonitis, treat as follows: Hold study treatment and treat with systemic corticosteroids and taper when the symptoms improve to grade 1 or less. For first occurrence, restart at the same dose with the same cycle length if AE improves to Grade 1 or less within 4 weeks when systemic steroid reduced to ~ prednisone 10 mg oral daily dose or less. If the symptoms improve to grade 1 or less between 4 to 8 weeks, discontinue therapy or consult with study chair. For second occurrence, discontinue study treatment and go to observation if $\geq$ 2 cycles of therapy were given, otherwise go to event monitoring.
	Grade 2		
	$\geq$ Grade 3		Discontinue study treatment and go to observation if $\geq$ 2 cycles of therapy were given, otherwise go to event monitoring. Recommend pulmonary evaluation including bronchoscopy and pulmonary function tests to rule out other causes. Treat with systemic

			corticosteroids. The use of infliximab may be indicated as appropriate. May consult study chair.
--	--	--	--

→ → Use the NCI Common Terminology Criteria for Adverse Events (CTCAE) version 4.0* unless otherwise specified ← ←			
CTCAE System/Organ/Class (SOC)	ADVERSE EVENT (at least possibly related)	AGENT	ACTION**
AT TIME OF RETREATMENT			
General disorders and administration site conditions	Infusion related reaction $\geq$ Grade 3 (see Section 9.9a for treatment guidelines)		Discontinue study treatment and go to observation if $\geq$ 2 cycles of therapy were given, otherwise go to event monitoring.
Immune system disorders	Immune system disorders – Other, specify Events of Clinical Interest & Immune-related Adverse Events (irAEs) (see Section 9.9b supportive care guidelines)	MK-3475	May hold study treatment. Steroid treatment may be indicated. Clinical AE resolves to grade 1 or less within 4 weeks: Same dose and schedule. Clinical AE does not resolve to grade 1 or less within 4 weeks: hold therapy until AE improves to grade 1 or less and may prolong the dosing interval to maximal 8 weeks. May increase the dosing interval by 1 week. May increase the dosing interval by 1 week for each occurrence. If AE does not resolve within 8 weeks of last therapy discontinue study treatment and go to observation if $\geq$ 2 cycles of therapy were given, otherwise go to event monitoring.
	Grade 2		Hold study treatment and discontinue if unable to reduce corticosteroid dose to $< 10$ mg per day prednisone equivalent within 8 weeks of adverse event. Consult with study chair as needed. If treatment is discontinued, go to observation if $\geq$ 2 cycles of therapy were given, otherwise go to event monitoring.
$\geq$ Grade 3 			

→ → Use the NCI Common Terminology Criteria for Adverse Events (CTCAE) version 4.0* unless otherwise specified ← ←			
CTCAE System/Organ/Class (SOC)	ADVERSE EVENT (at least possibly related)	AGENT	ACTION**
AT TIME OF RETREATMENT			
Investigations	Neutrophil count decreased Grade 4		Hold study treatment and restart when resolved to Grade 0-1 or baseline. May increase dosing interval by 1 week. If adverse event does not resolve to grade 0-1 or baseline within 8 weeks from last therapy, discontinue study treatment and go to observation if $\geq 2$ cycles of therapy were given, otherwise go to event monitoring.
Endocrine disorders	Adrenal Insufficiency Hyperthyroidism Hypothyroidism  Endocrine disorders - Other, Hypopituitarism, Thyroiditis, Hypophysitis  Grade 2	MK-3475	Monitor hormonal levels in the appropriate frequency by the discretion of treating physician until returned to baseline values. Hormonal replacement or other necessary therapy is recommended. Consider endocrine consultation as needed. Hold treatment until AE improves to grade 1 or baseline. If AE improves to grade 1 or baseline within 4 weeks, study treatment should be restarted at the same dose with the same cycle length for the first occurrence. The cycle interval will increase by one week for each occurrence of the same adverse events. If the treatment is delayed $\geq 8$ weeks, study treatment should be discontinued and go to observation if $\geq 2$ cycles of therapy were given, otherwise go to event monitoring.
	$\geq$ Grade 3		Hold study treatment, consider endocrine consultation and discussion. Rule out infection and sepsis with appropriate cultures and imaging. Consider treatment with corticosteroids 1 to 2 mg/kg daily. When symptoms improved to grade 1 or less, steroid taper may be started. Replacement of appropriate hormones may be required. Discuss with study chair for the option of continuation of treatment when the AE improves to grade 1 or baseline within 8 weeks from last therapy. If treatment is discontinued, go to observation if $\geq 2$ cycles were given, otherwise go to event monitoring.

→ → Use the NCI Common Terminology Criteria for Adverse Events (CTCAE) version 4.0* unless otherwise specified ← ←			
CTCAE System/Organ/Class (SOC)	ADVERSE EVENT (at least possibly related)	AGENT	ACTION**
AT TIME OF RETREATMENT			
Eye disorders	Uveitis Grade 1- 2	MK-3475	Hold treatment. Evaluation by an ophthalmologist is strongly recommended. Infectious causes will need to be ruled out. Treat with topical steroids is recommended. For the first occurrence, if AE resolves within 4 weeks, study treatment should be restarted at the same dose with the same cycle length. If AE resolves between 4-8 weeks from the last therapy, the cycle interval will increase by one week. Discontinue treatment if symptoms persist despite topical therapies. Discontinue treatment for the second occurrence. If the treatment is delayed $\geq$ 8 weeks, study treatment should be discontinued and go to observation if $\geq$ 2 cycles of therapy were given, otherwise go to event monitoring.
	$\geq$ Grade 3		Discontinue treatment. Evaluation by an ophthalmologist is strongly recommended. Infectious causes will need to be ruled out. Treat with topical or systemic steroids is recommended. When symptoms improve to grade 1 or less, systemic steroid taper should be started.
Cardiac disorders	Myocarditis Grade 1	MK-3475	Hold all treatment. Consult study chair. Resume when resolved and corticosteroids have been tapered, if applicable. If not resolved within 12 weeks of last dose or if corticosteroids cannot be reduced to $\leq$ 10 mg prednisone or equivalent per day within 12 weeks, discontinue treatment and go to observation if $\geq$ 2 cycles of therapy were given, otherwise go to event monitoring. Ensure adequate evaluation to confirm etiology and/or exclude other causes. .
	$\geq$ Grade 2		Discontinue all treatment and go to observation if $\geq$ 2 cycles of therapy were given, otherwise go to event monitoring. Ensure adequate evaluation to confirm etiology and/or exclude other causes. May administer corticosteroids.

Metabolism and nutrition disorders	Glucose intolerance (Type 1 diabetes mellitus [if new onset] or Hyperglycemia Any Grade	MK-3475	Hold treatment of MK-3475. Consult with endocrinology to decide if T1DM is confirmed. If T1DM confirmed, initiate insulin replacement therapy. Administer anti-hyperglycemic in participants with hyperglycemia. Monitor for hyperglycemia or other signs and symptoms of diabetes. Prior to restarting, consult with PI or treating physician to assess whether further treatment is indicated.
------------------------------------	---	---------	--

→ → Use the NCI Common Terminology Criteria for Adverse Events (CTCAE) version 4.0* unless otherwise specified ← ←			
CTCAE System/Organ/Class (SOC)	ADVERSE EVENT (at least possibly related)	AGENT	ACTION**
AT TIME OF RETREATMENT			
Other non-hematologic	Grade 2 Exception: Grade 2 alopecia and fatigue do not require any action.	MK-3475	Consider holding study treatment for persistent significant clinical symptoms until AE resolves to Grade 0-1 or baseline. Clinical AE resolves to grade 0-1 or baseline within 4 weeks: Same dose and schedule Clinical AE does not resolve to grade 0-1 or baseline within 4 weeks: May increase the dosing interval to maximal 8 weeks. May increase the dosing interval by 1 week for each occurrence. If AE does not resolve to grade 0-1 or baseline within 8 weeks, discontinue study treatment and go to observation if $\geq$ 2 cycles of therapy were given, otherwise go to event monitoring.
	$\geq$ Grade 3		Hold study treatment until AE resolves to Grade 0-1 or baseline. May increase the dosing interval by 1 week for each occurrence. Consult with study chair as needed. If AE does not resolve to grade 0-1 or baseline within 8 weeks from last therapy, discontinue study treatment and go to observation if $\geq$ 2 cycles of therapy were given, otherwise go to event monitoring. For any severe or life-threatening AE, consider discontinuing study treatment.

\* Located at [http://ctep.cancer.gov/protocolDevelopment/electronic\\_applications.ctc.htm](http://ctep.cancer.gov/protocolDevelopment/electronic_applications.ctc.htm)

\*\* Use the following to describe actions in the Action column:

- Hold/Delay = The current dose(s) of all drugs during a cycle is delayed. The patient does make up the delayed dose(s) when the patient meets the protocol criteria to restart drugs.
- Discontinue = The specified drug(s) are totally stopped.

**NOTES:**

- In case toxicity does not resolve to Grade 0-1 or baseline within 8 weeks after last infusion, trial treatment should be discontinued after consultation with the study chair. With study chair and Sponsor agreement, subjects with a laboratory or non-significant adverse event still at Grade 2 or baseline after 8 weeks may continue treatment in the trial only if asymptomatic and controlled with appropriate supportive care.
- Subjects who experience a recurrence of the same severe or life-threatening event at the same grade or greater with re-challenge of MK-3475 should be discontinued from trial treatment.

1. Consideration should be given to MK-3475 or Idelalisib as the causative agent in the setting of enterocolitis/pneumonitis, if both agents are being utilized. Consultation with the study chair is warranted.
2. In case of autoimmune hepatitis, when grade 3 (AST or ALT >5.0 times ULN and/or total bilirubin >3.0 times ULN), discontinue MK 3475 or combination therapy. Consider appropriate consultation and liver biopsy to establish etiology of hepatic injury. If necessary, treat with high-dose intravenous or oral glucocorticosteroids (prednisone equivalent 1-2 mg/kg) for 24 to 48 hours. When symptoms improve to grade 1 or less, a steroid taper should be started and continued. If serum transaminase levels do not decrease 48 hours after initiation of systemic steroids, oral mycophenolate mofetil 500 mg every 12 hours may be given.

**MK-3475 will be withheld for drug-related Grade 4 hematologic toxicities per table in 8.4, non-hematological toxicity  $\geq$  Grade 3 including uncontrolled laboratory abnormalities, and severe or life-threatening AEs as per Tables in 8.3 and 8.4**

8.4 MK-3475 Dose Modification for Hematological Toxicities (Platelet and Hemoglobin only) for MK-3475.

Note: hematological toxicity is not based on CTCAE 4.0 except neutrophil, but based on CLL specific hematological toxicity (this table and Appendix IV).

Dose modification guidelines for drug-related hematological (hemoglobin and platelets) adverse events

Toxicity	Grade 	Decrease from pretreatment 	Hold Treatment (Y/N)	Timing for restarting treatment	Dose/Schedule for restarting treatment	Discontinue Subject (after consultation with PI)
CLL/NHL specific Hematological 1 Toxicity (appendix IV)	1	11-24% decrease in HGB or PLT	No	N/A	N/A	N/A
	2	25-49% decrease in HGB or PLT				
	3	50-74% decrease in HGB or PLT	Yes	Toxicity resolves to Grade 0-2 or baseline	May increase the dosing interval by 1 week	Toxicity does not resolve within 8 weeks of last infusion Permanent discontinuation should be considered for any severe or life-threatening event. Go to observation if $\geq 2$ cycles of therapy were given, otherwise go to event monitoring
	4	$\geq 75\%$ decrease in HGB or PLT	Yes	Toxicity resolves to Grade 0-2 or baseline	May increase the dosing interval by 1 week	

If, at any level of decrease the platelet count is  $< 20,000/\mu\text{L}$ , this will be considered grade 4, unless the initial platelet count was  $\leq 20,000 \mu\text{L}$  in which case the patient is inevaluable for toxicity referable to platelet counts.

If, at any level of decrease from the baseline value the platelet and/or hemoglobin counts are within normal limits or platelet count is still  $\geq 100,000/\mu\text{L}$ , this will be considered a grade 0.

If patient has persistent cytopenia, it is recommended to repeat bone marrow evaluation to test if there is disease progression.

For patients initiated on combination therapy of a signal inhibitor with MK-3475, the pretreatment value is the value before addition of the signal inhibitor.

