#### Appendix IV Grading Scale for Hematologic Toxicity in CLL Studies

Decrease from Pretreatment value (%)	Grade 	
	Platelets 	Hemoglobin 
No change - 10%	0	0
11-24%	1	1
25-49%	2	2
50-74%	3	3
≥ 75%	4	4

1. A decrease in circulating granulocytes is not being considered since it is not a reliable index in CLL.
2. Grades: 1–mild; 2–moderate; 3–severe; 4–life-threatening. Grade 5 (fatal) toxicity can potentially occur at any level of decrease from pretreatment values and will be recorded as such.
3. If, at any level of decrease the platelet count is  $< 20,000/\mu\text{L}$ , this will be considered grade 4, unless the initial platelet count was  $\leq 20,000 \mu\text{L}$  in which case the patient is unevaluable for toxicity referable to platelet counts.
4. Baseline and subsequent hemoglobin determinations must be immediately prior to any given transfusions.
5. If, at any level of decrease from the baseline value the platelet and/or hemoglobin counts are within normal limits, this will be considered a grade 0.

\* Hallek BD, et al.: Guidelines for the diagnosis and treatment of chronic lymphocytic leukemia: a report from the International Workshop on Chronic Lymphocytic Leukemia updating the National Cancer-Institute- Working Group 1996 guidelines: Blood 111:54465456, 2008.

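### Minor: the closing sentence of Section 8.3 names only Grade 4 as a hematologic hold, but the 8.4 table it cites holds MK-3475 from grade 3

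*Combined protocol and SAP*

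**What the plan says.** The closing sentence of the notes to Section 8.3 lists three triggers for withholding MK-3475:

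- First: "MK-3475 will be withheld for drug-related Grade 4 hematologic toxicities per table in 8.4".
- Second: non-hematological toxicity at Grade 3 or above.
- Third: "severe or life-threatening AEs as per Tables in 8.3 and 8.4".

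Section 8.4 follows directly. Its heading limits it to "Dose Modification for Hematological Toxicities (Platelet and Hemoglobin only", and its note says that "hematological toxicity is not based on CTCAE 4.0 except neutrophil"; hemoglobin and platelets are graded on the CLL-specific scale of Appendix IV. In the table, grades 1 and 2 need no hold. Grade 3, "50-74% decrease in HGB or PLT", has Yes in the hold column, and so does grade 4. Both rows give the same condition for restarting: "Toxicity resolves to Grade 0-2 or baseline".

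Neutrophils are handled elsewhere. The Investigations row of the 8.3 table holds treatment for "Neutrophil count decreased Grade 4".

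**The concern.** The first clause tells the reader what the 8.4 table requires, and it gets the lowest hold grade wrong by one. The next clause uses Grade 3 or above for non-hematological events, so Grade 4 reads as a deliberate, higher threshold for blood counts.

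At stake is a missed hold. Someone working from the first clause alone could give MK-3475 to a patient with a drug-related grade 3 fall in hemoglobin or platelets, for whom the table says to hold. Cytopenia is plausible here: Section 3.19 admits patients with platelets as low as 25 x 10^9/L, and Arm A and C patients may add ibrutinib or idelalisib, for both of which Section 15 lists low platelets among the toxicities seen in roughly 10% of patients or more.

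**Working it through.** The plan gives no figure to reproduce, so the check is a comparison of texts with some grading arithmetic.

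**1. Clause against tables.**

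| Event | Where the rule is | Hold from | Named in the first clause? |
|---|---|---|---|
| Hemoglobin or platelets, grade 3 | 8.4 table | grade 3 | No |
| Hemoglobin or platelets, grade 4 | 8.4 table | grade 3 | Yes |
| Neutrophils, Grade 4 | 8.3 table | Grade 4 | Grade matches, but the table cited is 8.4 |

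The 8.4 table has 2 hold rows and the clause names 1 of them. The shared restart condition confirms that grade 3 is a hold level: recovery to grade 0-2 means recovery from grade 3 or worse.

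**2. Can the clause be read so that it is right?** If it means hemoglobin and platelets, the cross-reference is right and the grade is wrong. If it means neutrophils, the grade is right and the cross-reference is wrong. Either way it needs correcting.

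**3. Which platelet counts fall in the gap?** Let B be the baseline count. Grade 3 runs from 0.50 x B down to just above 0.25 x B, treating any fall short of 75% as grade 3. Footnote 1 of 8.4 makes a count below 20,000/uL grade 4 (unless the initial count was already at or below 20,000). Footnote 2 makes a count of 100,000/uL or more grade 0. The baselines below are illustrations, not figures from the plan.

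| Baseline (/uL) | 0.50 x B | 0.25 x B | Counts held by the table but not named in the clause |
|---|---|---|---|
| 200,000 | 100,000 | 50,000 | above 50,000 and below 100,000 |
| 100,000 | 50,000 | 25,000 | above 25,000, up to 50,000 |
| 50,000 | 25,000 | 12,500 | 20,000 to 25,000 |
| 40,000 | 20,000 | 10,000 | 20,000 only |

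For example, a fall from 100,000 to 40,000 is (100,000 - 40,000)/100,000 = 60%. Neither footnote applies, so it is grade 3 and the table says hold. For baselines above 20,000 and below 40,000 there is no gap, because a 50% fall already lands below 20,000 and counts as grade 4.

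**4. Does it reach the statistics?** The DLT definition in Section 16.4 covers hepatic toxicity, prolonged grade 4 non-hematological toxicity and any grade 5 event, so a grade 3 hemoglobin or platelet event is not a DLT under either reading. The stopping rules in 16.52 use that definition. The response endpoint in 16.11 and the decision rules in 16.2 do not refer to the hold threshold.

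**The case against.** The strongest defense is that the sentence, read whole, already covers grade 3. It is an additive list and does not say that Grade 4 is the only hematologic trigger. Its third clause brings in severe or life-threatening events under both tables, and Appendix IV labels the grades "3–severe; 4–life-threatening". On that reading the sentence and the table agree. The first clause also defers to the table, which comes next and has an explicit hold column. And because 8.4 replaces CTCAE for hemoglobin and platelets, nobody can grade such an event without consulting the CLL-specific scale.

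Most of this stands, and it rules out a stronger reading. A reader might infer that the protocol contains two conflicting hold thresholds, or that it permits dosing through grade 3 cytopenia. The documents do not support either. They state no general order of precedence between text and tables, but the clause's own reference sends the reader to the table, and the third clause points the same way.

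The defense does not make the first clause correct. To undo what it implies, the reader has to join a later clause to an appendix footnote. If the third clause already covers grades 3 and 4 under 8.4, the first adds nothing for hemoglobin and platelets except a misleading grade.

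**Conclusion.** The point holds as a minor error in current dosing text: one summary clause is incomplete and mis-referenced. The gap is one grade. A missed hold would need a reader who stops at the first clause and ignores both the rest of the sentence and the table cited.

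Reach is limited. Arms A and B are closed to accrual and Arm C plans 20 patients (Section 16.12), plus any Arm A or B patients still on treatment. The documents give no expected number of grade 3 hemoglobin or platelet events, so the number of holds at risk cannot be estimated.

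The conclusion assumes that the 8.4 table states the intended rule. Its explicit hold column and the restart condition shared by grades 3 and 4 support that.

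**What to change.** Replace the first clause so that the sentence begins:

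*MK-3475 will be withheld for drug-related Grade 3 or 4 hemoglobin or platelet toxicity per the table in 8.4, drug-related Grade 4 neutrophil count decreased per the table in 8.3,*

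and then continues with the existing non-hematological clause and the remainder unchanged. Keep the drug-related qualifier on both items. The 8.4 table is limited to drug-related events and the 8.3 table to events at least possibly related, so dropping it would extend holds to unrelated cytopenias and create a new mismatch.

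The cost is one clause in the next amendment. Neither table, the design nor the analysis changes.
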